### **Inclusion and Exclusion Criteria/Study Population**

Each patient will be screened prior to the procedure to determine if he or she is a candidate for trans-radial access. The screening process will consist of a Barbeau's test wherein a plethysmographic sensor is placed on the thumb or index finger of the upper extremity to be used during the procedure and the radial and ulnar arteries are simultaneously compressed. Once the pc waveform is absent, the pressure on the ulnar artery is released and the plethysmographic waveform is observed. Based on the morphology of the plethysmographic waveform, the patients are subdivided into 4 types: types A through C are considered candidates for transradial access while type D is considered a contraindication. As part of the screening process the patient's radial artery will also be evaluated with ultrasound to ensure that the diameter of the vessel is greater than or equal to 1.6 mm. The coagulation parameter of the patients, in particular the platelet count, INR and prothrombin time. In addition, due to inherent risk of radiation exposure associated with the angiographic procedure all premenopausal female patients will be screened with a urine hCG test.

To be included in the study patients will need to be:

- Age 18 years and older
- Have an acceptable Barbeau test (i.e. type A through C)
- Have acceptable coagulation parameters (based on PT, INR, platelet count, and appropriate pre-procedural management of anticoagulants, See Table 1)
- The caliber of the radial artery based on a pre-procedure sonographic evaluation will need to be greater than or equal to 1.6 mm.
- The appropriate pre-procedural management of anticoagulants is based on the consensus guidelines established by Patel et al.

Lab	Acceptable Range
INR	Less than 1.5
Platelet count	Greater than 50,000 platelets/ $\mu$ L
Prothrombin Time	Less than 15 seconds

Table 1. Acceptable Ranges of PT, INR and platelet count.

Patients will be excluded from the study if:

- If there is an unacceptable risk of bleeding diathesis, or
- If he or she is not a suitable candidate for transradial access based on a Barbeau test type D or a diameter of the left radial artery less than 1.6 mm.

There will be no exclusions based on gender/sex or race/ethnicity of the study participant.

## **Number of Subjects**

The study cohort will consist of up to 30 enrolled and randomized patients age 18 years and older who undergo an angiographic procedure via the radial artery. The proposed study does not include children.

## **Setting**

The setting of the study will be the Vascular and Interventional Radiology (VIR) Department at the Medical University of South Carolina. The VIR Department performs procedures at both the University Hospital and the Ashley River Tower. In addition, [name] has weekly outpatient clinics at the North Charleston Medical Pavilion ([name]) and East Cooper Medical Pavilion ([name]).

## **Recruitment Methods**

Subjects scheduled for angiographic procedures will be asked by the PI, Co-I or IRB approved study team members to participate in the trial. Eligibility will be determined by laboratory test and medication review.

## **Consent Process**

Once a patient is referred to Vascular and Interventional Radiology for consultation of an angiographic procedure that could be performed via the left or right radial artery, the patient will be informed of the study design by the PI, Co-I or IRB approved study team members. Some consents may be obtained prior to this during the initial consultation, but due to COVID precautions, consultations are mostly being conducted via telemedicine. We are not seeking obtain consent via tele methods. The recovery bay is great place to conduct this discussion due to privacy and that family members are often present. Patients are in prep bay for up to and over an hour prior to the procedure. The relative risks, benefits, and alternatives of the different approaches to attain hemostasis will also be discussed in detail. Informed consent will be obtained and appropriately documented in the patient's medical records. During the informed consent, it will be emphasized that regardless of the approach to hemostasis, the technical success of the intended procedure should not be affected.

The consent will be obtained at the time of the initial consultation. As stated above, no patients less than 18 years of age will be included in the study. On the day of the procedure, the design of the study and the relative risks, benefits, and alternatives of the different approaches to attain hemostasis will again be discussed in detail with the patient or patient's next of kin/medical power of attorney.

## **Study Design/Methods**

Following approval of the methodology by IRB we will conduct a randomized, single center study of up to 30 subjects who undergo an angiographic procedure via the radial artery. Those patients who meet the inclusion criteria will be randomly assigned to one of two groups (A or B) based upon a standard randomized process using pre-designated sealed envelopes.

Pre-procedure, all patients participating in the study will be evaluated with a Barbeau test and a sonogram of the radial artery to determine the caliber of the vessel (in mm) and the distance (in mm) from anterior wall of the vessel to the skin surface. In addition, updated INR, PT and platelet count (within 14 days) and if applicable pre-procedure management of anticoagulants will be reviewed. All these variables will be documented in the TR-Band Form.

Intra-procedure, all patients participating in the study will receive conscious sedation with midazolam and fentanyl - dosage at the discretion of the operator. Once the area around the puncture site is infiltrated with less than 1 mL of 1% lidocaine, the radial artery will be cannulated with a 21-gauge needle using a modified Seldinger technique (i.e. a single wall puncture). The needle will subsequently be exchanged over a 0.021-inch wire for a hydrophilic-coated 5 Fr x 10 cm Glidesheath Slender sheath. Patients will then receive 200 micrograms of intra-arterial nitroglycerin and an initial bolus of 3000-5000 units of intra-venous heparin. Of note, patients undergoing a transradial uterine artery embolization will also receive 2.5 mg of intra-arterial verapamil. During the procedure patients will receive additional boluses of 1000 units of intra-venous heparin at 30-minute intervals. Prior to removal of the sheath, a second dose of 200 micrograms of intra-arterial nitroglycerin will be administered and an ACT value will be measured. After the sheath is removed, hemostasis will be attained with a TR-Band. The TR-Band consists of a part-rigid, Velcro-secured wristband with an inflatable bladder that provides compression of the radial artery when air is injected into the cuff-valve system via the supplied syringe.

Group A (Total time about 60 minutes)	Group B (Total time about 120 minutes)
TR-Band Placed following your procedure	TR-Band Placed following your procedure
After 15 minutes deflated by 1/4	After 60 minutes deflated by 1/4
After 25 minutes deflated by 1/2	After 75 minutes deflated by 1/2
After 35 minutes deflated by 3/4	After 90 minutes deflated by 3/4
After 45 minutes deflated completely	After 105 minutes deflated completely
Observe your wrist for 15 minutes	Observe your wrist for 15 minutes
Remove TR-Band after 60 minutes	Remove TR-Band after 120 minutes

If bleeding were to occur, the TR-Band will be re-inflated to the previous volume and the weaning protocol will be restarted after 15 minutes. Once the TR-Band is removed the patient will be re-evaluated for complications including hematoma, ecchymosis and occlusion.

Post-procedure, patients will return to the clinic 1 month following their procedure and be re-evaluated for radial access complications including hematoma, ecchymosis and occlusion; and for re-evaluation of the Barbeau test, and ultrasound.

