### **Study Endpoints**

The study participants will be randomly assigned into one of two groups; these groups will be defined based on the time from inflation to initiation of deflation of the TR-Band, i.e. the time to wean.

Group A (Total time about 60 minutes)	Group B (Total time about 120 minutes)
TR-Band Placed following your procedure	TR-Band Placed following your procedure
After 15 minutes deflated by 1/4	After 60 minutes deflated by 1/4
After 25 minutes deflated by 1/2	After 75 minutes deflated by 1/2
After 35 minutes deflated by 3/4	After 90 minutes deflated by 3/4
After 45 minutes deflated completely	After 105 minutes deflated completely
Observe your wrist for 15 minutes	Observe your wrist for 15 minutes
Remove TR-Band after 60 minutes	Remove TR-Band after 120 minutes

The primary outcomes will be the incidence of significant hematomas (> 5 cm in size), bleeding (continued ooze requiring re-inflation of the TR-Band or subcutaneous ecchymosis without a discernable hematoma) and occlusion of the left radial artery (based on ultrasound) at the procedure visit and at one month follow up visit

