## **Risks to Subjects**

The potential risks to subjects for both groups include access site hematoma, pain, radial artery occlusion, and prolonged PACU recovery time. Potential transradial procedural related complications including pseudoaneurysm, digital ischemia, and arterial dissection are not inherently related to the timing of TR-Band deflation.

Per institutional protocol, the subjects will receive standard of care treatment as any similar patient in the same clinical scenario. Each planned procedure will involve a preprocedural evaluation including a sonogram of the radial artery that will be accessed during the procedure and Barbeau test conducted by the co-investigators under the supervision of the principal investigator. The Barbeau test will serve to rule out vascular compromise that may occur in the absence of sufficient vascular pressure. Not subject will be discharged until this is confirmed. Pre- and post-procedural laboratory values, including platelet count, activated clotting time and coagulation profile, will also be reviewed and analyzed. Following each procedure,

the subjects will be monitored for any immediate adverse events per the standard of care. As stated above, following discharge, the patient will be provided instructions as well as the contact information of the Nurse Coordinator for routine scheduling and care issues. In the case of an emergency, a Vascular and Interventional Radiology team of physicians and staff are on call 24 hours to manage any acute or emergent patient issues. All adverse events will be monitored, resolved, and recorded in the patient's medical record. Each case will be reviewed by PI or Co-I and IRB approved study staff to evaluate unanticipated problems or adverse events. These will be reported to IRB within 10 business days. An experienced VIR nurse, [name] will serve as an independent evaluator of each case to determine if unanticipated problem and adverse event might warrant the cessation of the study. The independent evaluator is not part of the IRB approved study team and will not be part of the publication of the findings. She will remain blinded to the unique study ID and will only have access to standard of care procedures and non-study data.

There is also a risk of loss of confidentiality. Being randomized to the expedited deflation group may be an additional risk.

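### Nothing in the plan keeps the assigned group from whoever assesses the one-month primary outcomes

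*Combined protocol and SAP*

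**What the plan says.** **Allocation.** Study Design/Methods has patients "randomly assigned to one of two groups (A or B) based upon a standard randomized process using pre-designated sealed envelopes". The allocation ratio is not given, and no masking after assignment is described.

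**Schedules.** The first deflation is at 15 minutes in Group A and at 60 minutes in Group B. Group A's table ends with "Remove TR-Band after 60 minutes"; Group B's band comes off at 120 minutes.

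**Outcomes.** Study Endpoints lists three primary outcomes: hematoma over 5 cm, bleeding (ooze needing re-inflation, or ecchymosis without a hematoma), and "occlusion of the left radial artery (based on ultrasound) at the procedure visit and at one month follow up visit".

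**One-month visit.** Study Design/Methods states that "patients will return to the clinic 1 month following their procedure and be re-evaluated for radial access complications including hematoma, ecchymosis and occlusion", and adds a repeat Barbeau test and ultrasound. No assessor is named.

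**Blinding.** The word appears once, in Risks to Subjects, for an independent nurse who judges whether events might warrant stopping the study: "She will remain blinded to the unique study ID and will only have access to standard of care procedures and non-study data". The patient codes in Data Management are for anonymization.

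**The concern.** On the procedure day the group cannot practicably be hidden from recovery staff, who see when the band is deflated and removed. One month later the band is long gone, and the person examining the wrist or reading the ultrasound has no need to know the group. The plan does not use that opportunity.

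Three features make this matter here.

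- **Room for judgement.** Ecchymosis counts as an event with no size threshold. Occlusion is based on ultrasound, but no criterion is given for calling it. Hematoma has a numeric cut-off, which leaves less room, though sizes near 5 cm still need a decision.
- **A stated expectation.** The Background sets out to establish earlier deflation as a preferable method, and Objectives/Specific Aims hypothesizes that the time to wean can be safely shortened.
- **A safety claim built on few events.** The favourable result is a low complication count in Group A, so under-calling even one event there would support the hypothesis.

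**Working it through.** **The plan's own figure.** The only design figure is the ceiling of 30 patients (Number of Subjects). It comes with no alpha, power, effect size or margin, so it cannot be reproduced. The point itself rests on the text; the arithmetic below only shows how sensitive the comparison is.

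**Step 1: what the text covers.**

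| Question | Where it would be answered | What is there |
|---|---|---|
| Who randomizes and deflates the band? | Study Design/Methods | Not stated |
| Who does the pre-procedure sonogram and Barbeau test? | Risks to Subjects | Co-investigators, supervised by the principal investigator |
| Who makes the one-month readings? | Study Design/Methods | Not stated |
| Is that person unaware of the group? | Anywhere | Not stated |
| Who is blinded, and to what? | Risks to Subjects | The safety evaluator, to the study ID |

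**Step 2: weight of one reading.** Assume 1:1 allocation, so 30/2 = 15 per arm. One reclassified patient changes an arm's rate by 1/15 = 6.7 percentage points.

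**Step 3: expected events.** The only event rate in the documents is 6% occlusion, from the early coronary series in the Background. At that rate:

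- Expected occlusions per arm: 0.06 × 15 = 0.9.
- Probability of none in an arm: 0.94^15 = 0.40.

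If Group A had one true occlusion and it was read as patent, its rate would go from 1/15 to 0/15.

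**Step 4: effect on the odds ratio.** Suppose the true rate p is the same in both arms, Group B is read correctly, and an unmasked reader records only a fraction s of Group A events. The expected-rate odds ratio is [sp/(1 − sp)] / [p/(1 − p)]. The values s = 0.5 and 0.8, and true rates of 20% and 30%, are assumptions.

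| True rate p | s = 0.8 | s = 0.5 |
|---|---|---|
| 6% | 0.79 | 0.48 |
| 20% | 0.76 | 0.44 |
| 30% | 0.74 | 0.41 |

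Check for 6% and s = 0.5: (0.03/0.97)/(0.06/0.94) = 0.48. The unbiased value is 1.0 throughout.

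**Step 5: effect on a test.** The two arms are independent, so Fisher's exact test is used here for illustration in place of the planned McNemar test. Two-sided p is 0.0996 for 4 events against 0, and 0.0421 for 5 against 0. One reading can therefore cross 0.05, but only in lopsided results. With equal true rates of 6%, the chance of p ≤ 0.05 is about 0.001 whether or not Group A events are under-read. At 30% with s = 0.5 it rises from 0.017 to 0.078. At low event rates the damage falls on the estimate and the event counts, and hardly at all on the significance test.

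**The case against.** The strongest reply is that this is silence in a small single-center protocol, and silence is not evidence of biased practice. Occlusion is an ultrasound finding, hematoma has a cut-off, and ooze needing re-inflation can only arise while the band is on, where masking is impractical anyway. Any misreading would also be small beside chance. For example, 4/15 against 2/15 gives an odds ratio of (4 × 13)/(11 × 2) = 2.36, with an approximate 95% interval of 0.36 to 15.5 and a Fisher p of about 0.65.

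Much of this stands. It limits the size of the point and rules out several stronger readings that a reader might infer:

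- **That the treating team makes the one-month readings with the records in hand.** The documents do not say so. The passage on a "Barbeau test conducted by the co-investigators under the supervision of the principal investigator" describes the pre-procedure evaluation only. The TR-Band Form is described as holding pre-procedure variables, so nothing shows that it reveals the group.
- **That the trial is declared open-label.** The term is not used; openness is inferred from the schedules and the absence of masking.
- **That Barbeau readings threaten the primary comparison.** The Barbeau test is repeated at one month but is not a listed primary outcome.
- **That masking certainly needs no extra staff.** Recruitment Methods and Consent Process refer to several team roles, but there is no staffing plan, and Setting ties the weekly outpatient clinics to an individual clinician.
- **That masking would remove the bias.** Patients know when their band came off.

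What the reply does not answer is that one-month readings with undefined thresholds enter the primary comparison, and nothing stops the person making them from knowing the group. Wide intervals do not excuse an avoidable bias, since imprecision and bias add to each other.

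**Conclusion.** The concern holds as a gap in the design: the one-month primary outcomes are left without any protection from knowledge of the group. It should be corrected, but it does not invalidate the trial. The documents do not show that bias will occur or in which direction; under-calling in Group A is the direction the stated expectation would favour.

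Its size is 6.7 percentage points per reclassified patient, which assumes 15 per arm. The odds ratios of 0.41 to 0.79 rest on assumed misreading rates and, apart from the 6% row, on assumed event rates. They are illustrations, not predictions. The primary-outcome sentence is read as applying both visits to all three outcomes. If the visits qualify occlusion alone, the point still holds for the one-month ultrasound. The protocol's front pages were not available, so a masking statement there would change the conclusion.

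**What to change.** In Study Design/Methods, at the one-month visit:

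1. Name the role that does the ultrasound and wrist examination. Specify an existing team member who did not manage that patient's band and is not shown the assignment or the deflation times.
2. Ask patients not to disclose their group.
3. Where ultrasound images are already saved, at either visit, label them by patient code only. Have an existing investigator who is unaware of group read occlusion, and state that this masked reading is the one analysed.
4. State that procedure-day ooze, hematoma and ecchymosis, and any live procedure-day occlusion check, remain open-label. Checks made for patient care are unaffected.

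The cost is protocol wording and some care with rostering. It depends on a suitable team member being available. Because patients may reveal their group, the masked reading of coded images is the most secure part.

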## **Data Management**

The data from living human subjects will include the physical examination, laboratory, and ultrasound data collected both immediately before and after the procedure; these include the pre-procedure History and Physical note, the procedure report, nursing notes and clinic Progress notes.

Only IRB approved team members will have access to the records of the patient's involved, which should be effective in controlling the confidentiality of the study. Individual, unique patient codes will be utilized in an Excel data spreadsheet for anonymization and subsequent analysis. These patient codes will be stored in a separate, secure location at the VIR Research Coordinator Office. The patient's safety will be ensured by the following methods. Prior to discharge from the PACU the patients will be given the contact information of the VIR Nurse Coordinator and clinic for any concerns. In addition, in the case of emergency, a VIR team of physicians and staff are on call at all times (24/7) to manage any acute or emergent patient issues.

The patients' characteristics (e.g. demographic information) will be compared using a t-test or chi-squared tests. The primary outcomes, i.e. rates of complications will be compared using a McNemar's test. An odds ratio will be estimated and its 95% confidence interval reported. Associations between preoperative factors and complications will be evaluated using logistic regression with random effects to account for multiple observations per patient.

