## **Objectives/Specific Aims**

The specific aim of the study is to evaluate the safety and efficacy of initiating earlier TR-Band weaning following transradial access procedures, while minimizing access site complications including hematoma formation and radial artery occlusion (RAO).

The primary objective is to evaluate the rate and severity of complications (i.e. hematoma, ecchymosis and radial artery occlusion) from an expedited weaning protocol wherein the time to wean is reduced significantly.

The secondary objective is to identify potential risks factors for complications following early weaning of the TR-Band.

It is hypothesized that the time to wean of the TR-Band can be safely reduced while minimizing access site complications including hematoma formation and radial artery occlusion (RAO).

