The rationale for an expedited weaning protocol is based in part on the observation that after access of the femoral artery for an angiographic procedure the standard to attain hemostasis without the use of a percutaneous closure device is manual pressure at the puncture site for 15 minutes. Since the radial artery, in contradistinction to the femoral artery, is superficial and readily compressible due to the flat surface of the radius, it is counterintuitive that to attain hemostasis pressure at the radial puncture site, pressure would need to be maintained for 60 minutes. In addition, Pancholy et al concluded based on a retrospective study of 10 consecutive patients undergoing transradial coronary angiography that “shorter duration of hemostatic compression is associated with a lower incidence of early and chronic RAO, without increase in bleeding complications.”

The standard of care (control) group in the study will consist of the subset of patients wherein the time to weaning of the TR-Band is 60 minutes.

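### McNemar's paired test is planned for two separately randomized groups, so the primary p-value is undefined; as specified, the analysis also gives no limit against which to judge that weaning time can be safely reduced

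*Combined protocol and SAP*

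**What the plan says.** All references are to the combined protocol and SAP.

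- **Design.** Study Endpoints: "The study participants will be randomly assigned into one of two groups". The groups differ in the time from inflation to first deflation of the band. Study Design/Methods repeats the assignment to A or B, made by sealed envelope. Each patient gets one schedule.
- **Primary outcomes.** Study Endpoints lists large hematoma, bleeding and radial occlusion, assessed "at the procedure visit and at one month follow up visit".
- **Primary analysis.** Data Management: "The primary outcomes, i.e. rates of complications will be compared using a McNemar's test". The next sentence reads: "An odds ratio will be estimated and its 95% confidence interval reported".
- **Repeated observations.** These are mentioned only for the risk-factor analysis, which uses "logistic regression with random effects to account for multiple observations per patient".
- **Hypothesis.** Objectives/Specific Aims: "It is hypothesized that the time to wean of the TR-Band can be safely reduced while minimizing access site complications".
- **Size.** Number of Subjects allows up to 30 patients. The documents give no allocation ratio, significance level, power, margin or acceptable complication rate.

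**The concern.** McNemar's test compares two binary results within each pair and uses only the pairs that disagree. Two separately randomized groups contain no such pairs, so the plan names a primary test that cannot be carried out as stated. An analyst would have to invent a pairing or change the test after seeing the data. If the arms ended up unequal, some patients would also have to be left out.

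The second issue is an omission rather than an error. The hypothesis is about safety, while the planned between-group analysis is a difference test and an odds ratio with its interval. No limit says how large an increase would still count as safe. In a study this small, a non-significant result could be taken as reassurance that it does not give. The primary comparison also does not state which visit it uses, or which observation counts if a patient contributes more than one.

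**Working it through.** **Inputs.** The total of up to 30 is from Number of Subjects. Assumed, because the documents are silent: 15 per arm (1:1, all places filled) and a two-sided 5% level. Event counts and rates by arm are illustrative. The only occlusion rate in the documents is the 6% in Background, from a historical coronary series; it is not offered as a planning rate. The plan has no sample-size or power figure to reproduce.

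**Step 1: is there any pairing that would serve?**
- Procedure visit against one-month visit in the same patient: this tests change over time, not A against B.
- Repeat procedures in one patient: no plan gives a patient both schedules.
- Matching between groups: none is described.

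The same paragraph compares patient characteristics by t-test or chi-squared test, which treats the groups as independent.

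**Step 2: what an arbitrary pairing does.** Take 8/15 versus 2/15 and let c be the number of pairs in which both members have the event. The discordant pairs are 8 − c against 2 − c. The exact p is twice the binomial(10 − 2c, ½) tail:

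| c | Discordant | Exact p | Probability under random pairing |
|---|---|---|---|
| 0 | 8 vs 2 | 2(1+10+45)/1024 = 0.109 | 21/105 = 0.20 |
| 1 | 7 vs 1 | 2(1+8)/256 = 0.070 | 56/105 = 0.53 |
| 2 | 6 vs 0 | 2/64 = 0.031 | 28/105 = 0.27 |

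The unpaired tests give one answer each for the same counts: Fisher 0.050, Pearson 0.020.

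**Step 3: what a non-significant result would leave open.** Newcombe's interval for the risk difference combines the Wilson limits (l, u) of each arm:

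lower = d − √[(p_A − l_A)² + (u_B − p_B)²]; upper = d + √[(u_A − p_A)² + (p_B − l_B)²].

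- 3/15 versus 0/15: the Wilson limits are 0.070 to 0.452 and 0 to 0.204. The difference is +20 points, with interval −4 to +45 points. Fisher p = 2 × 455/4060 = 0.22; Pearson p = 0.07.
- 0/15 versus 0/15: Newcombe gives −20 to +20 points. The exact upper limit per arm is 1 − 0.025^(1/15) = 21.8%. The odds ratio is 0/0, so there is no estimate. The chance of no events in 30 patients is (1 − p)^30: 0.156 at p = 6%, 0.042 at 10% and 0.001 at 20%.

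**Step 4: chance of a significant difference** (exact enumeration).

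| True rates | Per arm | Fisher | Pearson |
|---|---|---|---|
| 10% vs 30% | 15 | 15% | 28% |
| 10% vs 30% | 12 | 10% | 20% |

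From a 6% base with 15 per arm, Fisher's test reaches significance with probability 1.1% against 12%, 5.0% against 18% and 24% against 30%. The pooled normal approximation gives 8%, 17% and 40%.

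**The case against.** The mismatch between test and design has no good defence: no reading of the text supplies pairs. The case on the other side concerns the rest, and much of it stands.

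- **The interval could support a safety statement.** A reader might infer that the planned analysis cannot address safety at all. The documents do not support that. A 95% confidence interval is promised, and it would serve if judged against a limit fixed in advance. What is missing is the limit.
- **Nobody says that non-significance means safety.** A reader might infer that the investigators intend this. The text does not say so, and the primary objective, to evaluate the rate and severity of complications, is one of estimation. It remains true that nothing in the plan rules the reading out.
- **The pairing example uses high rates.** Background calls complications rare. With no events in one arm there are no event-event pairs, and the McNemar p-value does not depend on pairing: 3 against 0 gives an exact p of 0.25 however patients are paired. So the numerical effect may be small at low rates. Bleeding here includes ooze and ecchymosis and may be commoner, but no rate is given.
- **Prior evidence is reassuring.** Intervention to be Studied quotes a retrospective study in which "shorter duration of hemostatic compression is associated with a lower incidence of early and chronic RAO, without increase in bleeding complications". The protocol describes it as based on 10 patients. That is too thin to set aside any of the three primary outcomes, and it is the expectation this trial would check.

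**Conclusion.** The choice of McNemar's test is wrong as written. The groups are independent, no pairs exist, and the primary p-value is undefined. This conclusion needs no assumption about rates or allocation. When both arms have events, the size of the problem can be decisive: the same 8/15 versus 2/15 crosses the 5% line or not by pairing alone.

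The safety part holds in a limited form. As specified, the difference test and odds ratio do not by themselves support the hypothesis, for three reasons: there is no limit for the interval, a non-significant result is likely with up to 30 patients, and the odds ratio fails if neither arm has an event. The unstated visit and unit of analysis are missing detail. These figures rest on 15 per arm, a two-sided 5% level and illustrative rates; with 12 per arm the picture is slightly worse.

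A reader might go further and conclude that the trial's data will be unusable, or that the hypothesis must be withdrawn. Neither follows. The data can be analysed validly by an unpaired method, and rewording the hypothesis is a matter of preference. The point should be fixed before analysis.

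**What to change.** In Data Management, replace the McNemar sentence by:

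> For each primary outcome, at the procedure visit and at one month separately, Groups A and B will be compared as independent groups, using each patient's first randomized procedure and all patients assessed at that visit: the risk difference (A minus B) with a 95% Newcombe interval, and each group's rate with exact 95% limits. Any p-value will come from an unpaired test (Fisher's exact).

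Keep the odds ratio as a secondary summary, and add:

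> A non-significant difference will not be taken as evidence of safety; any statement on safety will quote the upper confidence limit.

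Rewording the hypothesis in Objectives/Specific Aims as an estimation aim is optional.

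**Cost.** Protocol wording only, with no extra patients, visits or data. Three outcomes at two visits give six intervals, none of which this wording puts first. The main downside is that the permitted conclusion is weaker than 'safe'.
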